The ITV treatment arm patients who are discontinued from study treatment prematurely will be asked to undergo the scheduled monthly assessments until Last Patient In (LPI) Month 9 visit, after which they will be scheduled 30 (+7) days later for their final study visit. The patients who are discontinuing study treatment from the Implant treatment arms will be scheduled, within 7 days after the treatment discontinuation decision is made, for Implant explantation followed by safety visits 1 and 7 ( $\pm 2$ ) days post-explantation. Afterwards, they will be followed in the study, attending their monthly scheduled visits, until LPI Month 9 visit, after which they will be scheduled for the early termination visit (see [Appendix 1](#)). As per investigator judgement, these patients may start an approved anti-VEGF for their AMD once the need for Implant explantation is confirmed and, preferably, after explantation is completed. All explanted Implants with their remaining content will be returned to the designee of the Sponsor for storage and potential future exploratory analysis (see Section 4.4). A vitreous or aqueous humor sample will be collected at the start of explantation for patients undergoing an explantation procedure (see [Appendix 19](#)).

Patients who withdraw from the study prior to scheduled study completion will be asked to return for an early termination evaluation 30 (+7) days following their last study treatment for monitoring of adverse events and early termination visit assessments if they are in the ITV treatment arm. The patients who are discontinuing the study from the Implant treatment arms will be scheduled for Implant explantation within 7 days of the treatment discontinuation decision, followed by Safety Visits 1, 7 ( $\pm 2$ ), 30 ( $\pm 7$ ), and 60 ( $\pm 7$ ) days post-explantation after which they will be scheduled for the early termination visit 30 (+7) days later. As per investigator judgment, these patients may start an approved anti-VEGF treatment for their AMD once the need for Implant explantation is confirmed and, preferably, after explantation is completed. All explanted Implants with remaining content will be returned to the designee of the Sponsor for storage and potential future exploratory analysis (see Section 4.4). A vitreous or aqueous humor sample will be collected at the start of explantation for patients undergoing an explantation procedure (see Appendix 19).

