#### **4.6.10.3 Assessments at Early Study Treatment Discontinuation**

The ITV treatment arm patients who are discontinued from study treatment prematurely will be asked to undergo the scheduled monthly visits until the LPI Month 9 visit, after which they will be scheduled for their final study visit 30 (+7) days later. The patients who are discontinuing study treatment from the Implant treatment arms will be scheduled, within 7 days after the treatment discontinuation decision is made, for Implant explantation followed by safety visits 1 and 7 ( $\pm 2$ ) days post-explantation. Afterwards they will be followed in the study, attending their monthly scheduled visits, until LPI Month 9 visit, after which they will be scheduled for the early termination visit (see [Appendix 1](#)). As per investigator judgement, these patients may start an approved anti-VEGF for their AMD once the need for Implant explantation is confirmed and, preferably, after explantation is completed. All explanted Implants, with remaining

content, will be returned to the designee of the Sponsor for storage and potential future exploratory analysis (see Section 4.4). A vitreous or aqueous humor sample will be collected at the start of explantation for patients undergoing an explantation procedure (see [Appendix 20](#)).

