##### **4.4.2.1 Visual Acuity Change in Best Corrected Visual Acuity (BCVA)**

For change in BCVA from baseline, several supportive preliminary analyses will be performed as described below:

- Change from baseline in BCVA score averaged over Month 9 and Month 10 analyzed with an mixed effects repeated measures (MMRM) model
- Change from baseline in BCVA score averaged over Month 9 and Month 10 analyzed with a trimmed mean approach
- Change from baseline in BCVA score through Month 10 analyzed with an analysis of covariance (ANCOVA) model with missing data imputed by the last observation carry forward (LOCF) approach

- Change from baseline in BCVA score over time through Month 10 for patients treated after surgical Instruction for Use Version 10 (IFU v10) analyzed with descriptive statistics

The details for these analyses are provided as follows:

- Mixed effects with repeated measures (MMRM) analysis for change in BCVA score from baseline averaged over Month 9 and Month 10:

The change from baseline in BCVA score averaged over Month 9 and Month 10 will be compared between each PDS arm and the comparator intravitreal arm using a MMRM model. The model will include the change from baseline at Months 1 to 10 as the response variables and will include the categorical covariates of treatment group, visit, visit-by-treatment group interaction, the continuous baseline value for the response variable (in this case, baseline BCVA), as well as randomization stratification factors as fixed effects. Comparisons between each PDS and the intravitreal arm will be made using a composite contrast over Months 9 and 10. The MMRM model will assume an unstructured covariance structure. If there are convergence problems with the model, then a heterogeneous compound symmetry or a first order autoregressive (AR [1]) covariance structure may be fitted.

Best corrected visual acuity (BCVA) assessments will be censored after the time of rescue intravitreal anti-VEGF injection in the study eye and after the time of explant. Missing data will be implicitly imputed by the MMRM model, assuming a missing at random missing data mechanism (i.e., missing data are dependent on other observed variables but not on the missing data).

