An additional MMRM analysis will be performed including all observed measurements. That is, all observed BCVA data will be included regardless of whether patients received rescue treatment or discontinued study treatment due to AE or LCE. Best corrected visual acuity (BCVA) assessments at the time of explant will be censored. This analysis evaluates the treatment policy of PDS with rescue therapy versus the monthly intravitreal ranibizumab.

From the recent end of Phase II meeting with the US FDA on 23 March 2018, the Agency agreed that the change in BCVA from baseline averaged over Month 9 and Month 10 is an appropriate primary endpoint for the Phase III study to assess the non-inferiority (NI) in visual acuity between the Implant and intravitreal arms with an NI margin of 4.5 letters. This NI margin will be used as a reference to assist data interpretation in this preliminary assessment.

To support the interpretation of BCVA change from baseline over time, figures for the adjusted mean change from baseline over time through Month 10 will be provided.

- Trimmed mean analysis for change in BCVA score from baseline averaged over Month 9 and Month 10:

A trimmed mean analysis ([Permutt and Li 2016](#)) will be performed using an analysis of covariance (ANCOVA model) for adjustment for covariates. The dependent variable in the ANCOVA model is the average of Month 9 and Month 10

assessments in change from baseline in BCVA score (if one of the two assessments is missing, the non-missing assessment will be used), and the independent variables are the treatment group, baseline BCVA score (continuous), and the randomization stratification factor of baseline ( $\leq 65$  letters vs.  $\geq 66$  letters) and number of anti-VEGF-intravitreal injections ( $\leq 3$  vs.  $\geq 4$ ).

Patients will be considered to have the worst outcomes and will be trimmed from analysis if any of the following occurs:

- Patients in the PDS arm receive a rescue treatment (intravitreal injection) or undergo explantation prior to Month 9
- Patients in all treatment arms discontinue study treatment due to LCE or AE prior to Month 9
- Patients in all treatment arms have a missing Month 9 assessment and discontinue study treatment due to LCE or AE at Month 9
- Patients in all treatment arms have missing Month 9 and Month 10 assessments and discontinue study treatment due to LCE or AE at Month 10

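### The additional BCVA MMRM is labelled treatment policy but censors at explant, so on its natural reading almost all post-discontinuation vision is dropped in the PDS arms and kept in the ITV arm

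*SAP*

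**What the plan says.** SAP 4.4.2.1 plans two MMRM analyses of change in BCVA. In the main one, "assessments will be censored after the time of rescue intravitreal anti-VEGF injection in the study eye and after the time of explant". The additional one is meant to use every observed measurement, and the SAP spells this out: "all observed BCVA data will be included regardless of whether patients received rescue treatment or discontinued study treatment due to AE or LCE". The sentence after that reads: "Best corrected visual acuity (BCVA) assessments at the time of explant will be censored". The paragraph then gives the purpose: "This analysis evaluates the treatment policy of PDS with rescue therapy versus the monthly intravitreal ranibizumab".

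The protocol fixes what discontinuation means in the Implant arms. Under Protocol 3.1, and again under 4.6.10.3 and 4.7.2, patients "discontinuing study treatment from the Implant treatment arms will be scheduled, within 7 days after the treatment discontinuation decision is made, for Implant explantation". Those who stay in the study are still seen: "Afterwards they will be followed in the study, attending their monthly scheduled visits, until LPI Month 9 visit". ITV patients who stop treatment are also asked to keep their monthly visits up to that point. Protocol 4.7.2 adds that the sponsor supplies explanted patients with ITV ranibizumab until the LPI Month 9 visit, where applicable.

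The same SAP section adopts a 4.5-letter non-inferiority margin as a reference for interpretation. SAP 4.4.2 says there will be no formal testing of these contrasts and that differences come with 95% CIs.

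**The concern.** A treatment-policy analysis uses outcomes whatever happened to treatment, by the same rule in each arm. Here the inclusion rule covers discontinuation for an adverse event or lack of clinical efficacy. In the Implant arms, however, discontinuation leads to explantation within days, and explant is the censoring event. The exception therefore removes nearly everything the inclusion rule promises for PDS. ITV patients have no implant and so no matching censoring event.

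After censoring, the MMRM treats the later PDS values as missing at random and in effect fills them in from each patient's pre-explant vision and the pattern of the other patients. If explanted eyes do worse than that prediction, the PDS mean is too high, in the model-based analysis that claims to describe the policy and beside a 4.5-letter reference.

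**Working it through.** **1. What each rule does in each arm.**

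| Situation | PDS arms, additional MMRM | ITV arm, additional MMRM |
|---|---|---|
| Rescue, still on study treatment | kept | not applicable (rescue is defined for Implant patients) |
| Study treatment stopped, before explant (up to about 7 days) | kept | not applicable |
| Study treatment stopped, later visits | censored, on the natural reading | kept |

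Lack of clinical efficacy does not even this out. Its definition requires two consecutive Implant refills, so it cannot arise in the ITV arm. In the Implant arms its specified consequence is rescue and a refill, not discontinuation.

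**2. Whether another output fills the gap.** The LOCF ANCOVA also censors after explant. The trimmed-mean analysis ranks PDS patients explanted before Month 9 as worst outcomes and trims them, so their measured vision does not enter the estimate. The BCVA summary through the end of the study keeps post-explant data but is descriptive, with no adjusted between-arm difference. No planned model-based contrast clearly uses post-explant BCVA.

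**3. The plan's own precision figure.** SAP 2.3 gives SD 10 letters, 60 patients per Implant arm, 40 in the ITV arm, and an 80% CI extending 2.62 letters. Check: 1.2816 × 10 × √(1/60 + 1/40) = 1.2816 × 10 × 0.2041 = 2.62. It reproduces as the half-width for the between-arm difference. At the 95% level used for these contrasts: 1.96 × 10 × 0.2041 = 4.0 letters.

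**4. Size of the possible shift.** Let e be the share of an Implant arm explanted before Month 9. Let d be the number of letters by which these patients' true Month 9/10 change falls below the MMRM prediction. Replacing the true values by predictions raises the arm mean by about e × d. The ITV mean is unchanged, so the PDS-minus-ITV difference moves by the same amount. The documents state neither e nor d; the values below are assumptions.

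| e (patients of 60) | d = 5 | d = 10 | d = 20 | d = 30 |
|---|---|---|---|---|
| 2% (1.2) | 0.10 | 0.20 | 0.40 | 0.60 |
| 5% (3) | 0.25 | 0.50 | 1.00 | 1.50 |
| 10% (6) | 0.50 | 1.00 | 2.00 | 3.00 |

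Against 4.5 letters, the range runs from 0.1/4.5 = 2% to 3.0/4.5 = 67%.

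**The case against.** The strongest reply turns on one word. The additional MMRM censors *at* the time of explant, whereas the main MMRM and other rules in the section say *after*. Taken literally, only the explant-time value is dropped, later data stay, and the asymmetry disappears. That reading is possible. Censoring from explant onward is the more natural one, and a prespecified rule should not leave the choice open.

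Second, the label is treatment policy of PDS *with rescue therapy*. After explant the eye no longer has PDS and may receive the comparator drug, so treatment policy for rescue combined with censoring at explant could be a deliberate choice. The difficulty is that the SAP also names discontinuation for an adverse event or lack of efficacy as something that does not remove data. Under that interpretation the clause has almost no effect in the Implant arms.

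Third, the harm in explanted eyes can be overstated. Protocol Table 6 calls for explantation for observed Implant damage even without an adverse event, and for pregnancy. Vision loss recorded before explant enters the model and lowers the prediction, and post-explant ranibizumab may limit later loss. All of this stands, and it favours small values of d. Against it, Protocol 5.2.3 lists explantation among interventions to prevent permanent loss of sight, so some explanted eyes will be in trouble.

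Finally, these are supportive analyses without formal testing. That limits the consequence but does not remove the inconsistency.

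**Conclusion.** The inconsistency holds on the natural reading of the explant sentence: the additional MMRM is not treatment policy in both arms. Any resulting bias is plausibly toward PDS. Under the assumed ranges it is about 0.1 to 3.0 letters, with post-explant ranibizumab and explants unrelated to vision pointing to the low end. The point merits correction but does not touch the primary endpoint.

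A reader might infer more than the documents support:

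- **A demonstrated bias of known size.** Neither the explant rate nor the shortfall is given, and a large shortfall such as 30 letters is only the top of an assumed range.
- **That all explanted eyes are badly harmed.** The protocol's grounds for explantation do not show this.
- **That keeping ITV data after discontinuation adds to the bias.** Under treatment policy, keeping them is correct.
- **That the main MMRM must gain a matching ITV censoring rule.** Which strategy that analysis follows is a debatable estimand choice and is not part of this point.
- **That no post-discontinuation PDS data count at all.** Values between the decision and the explant, or from a patient never explanted, remain.

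**What to change.** In SAP 4.4.2.1, delete the explant-censoring sentence from the additional MMRM. State that all BCVA collected after explant, through Month 10, is included. This also settles the *at* versus *after* question for this analysis. Leave the main MMRM as it is.

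The SAP should note the limit of the data. Monthly visits after explant are promised only to the LPI Month 9 visit, so some Month 10 values will be missing for late enrollees. Patients who leave the study altogether have only post-explant safety visits and a termination visit. Some reliance on missing at random will remain.

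The change is to SAP wording and programming, with no new data collection. The likely price is a slightly less favourable and more variable PDS estimate.

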#### **4.6.10.4 Assessments at Early Study Discontinuation**

Patients withdrawing from the study early should return for an early termination evaluation 30 (+7) days following the last study drug treatment for monitoring of all adverse events (serious and non-serious), as well as for early termination assessments if they are in the ITV treatment arm. The patients who are discontinuing the study from the Implant treatment arms will be scheduled for Implant explantation within 7 days of the study discontinuation decision. This will be followed by Safety Visits 1, 7 ( $\pm 2$ ), 30 ( $\pm 7$ ), and 60 ( $\pm 7$ ) days post-explantation, after which they will be scheduled for the early termination visit 30 (+7) days later. As per investigator judgment, these patients may start an approved anti-VEGF treatment for their AMD once the need for Implant explantation is confirmed and, preferably, after explantation is completed. All explanted Implants, with remaining content, will be returned to the designee of the Sponsor for storage and potential future exploratory analysis (see Section 4.4). A vitreous or aqueous humor sample will be collected at the start of explantation for patients undergoing an explantation procedure (see [Appendix 20](#)).

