#### **4.7.3 Early Withdrawal from Study**

Every effort should be made to obtain information on patients who are withdrawing from the study. The primary reason for withdrawal from the study should be documented on the appropriate eCRF.

Patients withdrawing from the study early should return for an early termination evaluation 30 (+7) days following the last study drug treatment for monitoring of all adverse events (serious and non-serious), as well as for early termination assessments if they are in the ITV treatment arm. The patients who are discontinuing study from the Implant treatment arms will be scheduled for Implant explantation within 7 days of the treatment discontinuation decision, followed by Safety Visits 1, 7 ( $\pm 2$ ), 30 ( $\pm 7$ ), and 60 ( $\pm 7$ ) days post-explantation, after which they will be scheduled for the early termination visit 30 (+7) days later. As per investigator judgment, these patients may start an approved anti-VEGF treatment for their AMD once the need for Implant explantation is confirmed and, preferably, after explantation is completed. All explanted Implants, with remaining content, will be returned to the designee of the Sponsor for storage and potential future exploratory analysis (see [Section 4.4](#)). A vitreous or aqueous humor sample will be collected at the start of explantation for patients undergoing an explantation procedure (see [Appendix 19](#)).

The primary reason for premature study discontinuation (which may differ from study treatment discontinuation) should be documented on the appropriate eCRF. Patients who discontinue from the study prematurely will not be replaced and cannot re-enter the study.

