## **Appendix 21**

### **Ranibizumab Port Delivery System: Device Clinical Investigation Plan (cont.)**

#### **7.4 EXPECTED DROP-OUT RATES**

Less than 8% dropout rate is expected based on the previous clinical trials for ranibizumab. Thus, an 8% dropout rate is assumed in the above sample size section for Implant clogging data analysis.

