Such patients will be referred to as "must be trimmed patients." For the remaining patients, if they have Month 9 and/or Month 10 BCVA assessments, they will be considered "completers"; if they have missing Month 9 and Month 10 assessments, the missing data will be considered missing at random, and these patients will be removed from the analysis.

The inferential statistics (i.e., 95% CI) for the trimmed mean will be based on the permutation test. The treatment assignments will be permuted in a sufficiently large random sample of possible ways (~30,000 random samples will be generated).

The algorithm can be stated in the following four steps:

1. Remove patients whose missing assessments are considered missing at random (see definition above) from the analysis.
2. Order the data based on adjusted values from the ANCOVA model, and trim equal fractions (i.e., a pre-specified fraction for fixed trimming) from both treatment arms

The adjusted values are determined as follows. An ANCOVA model as specified above will be fitted for all completers. The estimated treatment effect will be discarded and the coefficients for the covariates will be kept to calculate the adjusted value  $Y - b'X$  for each patient, for which  $Y$  is the change in BCVA score averaged over Month 9 and Month 10,  $X$  is the matrix for the covariates—baseline BCVA score (continuous) and the baseline BCVA score ( $\leq 65$  letters vs.  $\geq 66$  letters) and number of anti-VEGF-intravitreal injections ( $\leq 3$  vs.  $\geq 4$ ), and  $b$  is the estimated coefficient matrix for the covariates.

These adjusted values will be used to rank the data within each treatment group. The "must be trimmed" patients will always be ranked the lowest (regardless of whether their adjusted values are available) and trimmed from

the analyses. The best (1-trimming fraction)\*100% in each group will be used for the analysis specified in Step 3.

3. Refit the ANCOVA model (as specified above) to the trimmed data set, and compute the difference in trimmed mean between two treatment groups.
4. Repeat Steps 2 and 3 on each permuted data to construct a reference distribution for confidence interval estimation for the difference in trimmed mean.

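### The trimmed-mean BCVA analysis ranks any recorded PDS explantation before Month 9 as a worst outcome whatever the reason, while the same non-AE, non-LCE exit from the ITV arm is not

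*SAP*

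**What the plan says.** SAP 4.4.2.1 lists four situations in which a patient is assumed to have a worst outcome and must be trimmed. The first is for PDS patients only: "Patients in the PDS arm receive a rescue treatment (intravitreal injection) or undergo explantation prior to Month 9". The other three cover every arm and depend on the reason; the leading one reads "Patients in all treatment arms discontinue study treatment due to LCE or AE prior to Month 9". The other two apply the same LCE-or-AE condition at Month 9 and Month 10 when assessments are missing.

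Patients in none of these groups are completers if they have a Month 9 or Month 10 value. Otherwise "the missing data will be considered missing at random, and these patients will be removed from the analysis". Must-be-trimmed "patients will always be ranked the lowest (regardless of whether their adjusted values are available"). Equal fractions are then cut from the two arms being compared. The fraction is the percentage meeting the criteria, rounded up to the nearest 5%.

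On the protocol side, explantation is part of the exit route. Section 4.6.10.4 says Implant patients "discontinuing the study from the Implant treatment arms will be scheduled for Implant explantation within 7 days of the study discontinuation decision"; sections 3.1 and 4.7.3 agree. Sections 4.6.10.3 and 4.7.2 schedule explantation for Implant patients who stop treatment but stay in follow-up. None of these sections makes it depend on the reason. An ITV patient who stops treatment is asked to continue monthly visits.

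**The concern.** The SAP separates exits that signal failure (LCE, AE) from exits that do not, and then drops that distinction for explanted PDS patients. Take two patients who leave at Month 5 because they are moving away, both seeing well. The PDS patient is explanted on the way out and is ranked lowest. The ITV patient has no Month 9 or Month 10 value and is removed as missing at random. If both stop treatment but remain in follow-up, the PDS patient is still ranked lowest even with BCVA on record, while the ITV patient can be a completer. In these cases the rule scores the exit procedure and not the visual outcome, although the SAP's stated aim is to compare the arms with true or assumed worst outcomes excluded.

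The consequence is directional. Each such PDS exit uses up a trimming slot, so a poor observed PDS result stays in the mean while the ITV result of the same rank is cut. At stake is the estimated BCVA difference from one of the analyses that inform Phase III planning. The SAP gives 4.5 letters as an interpretive reference for the preliminary BCVA assessment.

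**Working it through.** **Inputs.** SD 10 letters, 60 patients per PDS arm and 40 in ITV (SAP 2.3). Total dropout: "Less than 8% dropout rate is expected based on the previous clinical trials for ranibizumab" (Protocol Appendix 21, section 7.4, stated for the clogging analysis). The documents do not split dropout by reason, so non-AE, non-LCE withdrawal with recorded explantation before Month 9, *w*, is an assumption: 2%, 4%, and 8% as the ceiling. Also assumed: normally distributed outcomes, no true difference, *w* equal in both arms and unrelated to outcome.

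**Plan's own figure.** 1.2816 × 10 × √(1/40 + 1/60) = 2.62 letters. This reproduces the stated 80% CI half-width and confirms that SD 10 and 60 versus 40 are the planning inputs for the BCVA comparison.

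**Method.** The mean of a normal variable with its lowest fraction *q* removed is 10 × φ(z_q)/(1 − q).

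- ITV: withdrawals are removed first, so the full trimming fraction *f* is cut from observed values and q = f.
- PDS: withdrawals fill *w* of the slots, so only q = (f − w)/(1 − w) of observed values is cut.

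**Example, f = 10%, w = 8%.** ITV: 10 × 0.1755/0.90 = 1.95. PDS: q = 0.02/0.92 = 0.0217, giving 10 × 0.0520/0.9783 = 0.53. Difference 0.53 − 1.95 = −1.42 letters.

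| f | w | PDS q | PDS mean | ITV mean | Shift (letters) |
|---|---|---|---|---|---|
| 10% | 2% | 0.0816 | 1.64 | 1.95 | −0.31 |
| 10% | 4% | 0.0625 | 1.31 | 1.95 | −0.64 |
| 10% | 8% | 0.0217 | 0.53 | 1.95 | −1.42 |
| 5% | 2% | 0.0306 | 0.71 | 1.09 | −0.37 |
| 5% | 4% | 0.0104 | 0.28 | 1.09 | −0.81 |

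The 5% rows apply the SAP's rounding when these exits are the only trimmed patients. The 10% rows at 2% and 4% are what the rounding gives if a further 5% in each arm are genuine worst outcomes. With that further 5%, the 8% case rounds to f = 15% and the shift is −1.19.

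**Sensitivity to how *f* is set.** The SAP does not say whether the percentage is taken per arm or across both. Across both at w = 8%, it is 4.8 of 100, rounded up to 5%. That is below the PDS share of 8%, so the fraction rises to 8%. PDS then loses no observed values and ITV loses 8%: 0 − 10 × φ(z_0.08)/0.92 = −1.62. A 60-versus-40 simulation on this reading (8,000 runs) gave −1.65.

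**Same-rule check.** If these exits are removed in both arms, q is equal and the shift is 0 in closed form; simulation gave at most about 0.05 letters.

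**The case against.** A reader might infer that every PDS withdrawal is scored as worst. The documents do not support that. The protocol says withdrawing Implant patients will be scheduled for explantation; the SAP trims those who undergo it before Month 9. Protocol 4.7.1 ends follow-up once consent is withdrawn. A PDS patient who is lost or withdraws without a recorded explantation falls under "if they have missing Month 9 and Month 10 assessments, the missing data will be considered missing at random", as in ITV.

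A reader might also take 1.4 letters, about 30% of the 4.5-letter reference (1.42/4.5 = 32%), as the expected distortion. That requires the whole 8% ceiling to be non-AE, non-LCE and explanted before Month 9, which the documents do not say. At 2 to 4% the shift is small beside the 95% CI half-width of an untrimmed comparison, 1.96 × 10 × √(1/40 + 1/60) = 4.0 letters.

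It can be argued that losing the implant is itself a treatment failure, and explantation is a listed exploratory outcome (SAP 2.2.5). That would be a coherent definition, but the other three criteria tie failure to LCE or AE, and the explantation clause also captures exits unrelated to either. It can also be said that the MMRM, which censors BCVA after explant, and the LOCF ANCOVA do not rank these patients worst. That is true, but they are different estimators and do not correct this one. The optional sensitivity analyses vary only the trimming percentage.

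Three points stand. The analysis is supportive, with no formal testing. The bias runs against PDS, so it cannot create a favourable implant result. Narrowing the criterion now would come after two unmasked interim efficacy analyses.

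**Conclusion.** The asymmetry is in the text and nothing elsewhere in the plan removes it. It is confined to PDS patients with a recorded explantation before Month 9 for a reason other than AE or LCE. Under the stated assumptions it moves the trimmed-mean difference against PDS by about 0.3 to 0.6 letters at 2 to 4% withdrawal with 10% trimming, or 0.4 to 0.8 with 5% trimming. At the 8% ceiling the figure is about 1.4 letters (1.6 if the fraction is taken across both arms). These sizes are illustrations resting on assumed withdrawal rates and normal outcomes; the direction follows from equal trimming fractions.

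The time-to-first-refill primary endpoint is unaffected, and no formal conclusion depends on this analysis. The rule should still be corrected, because it puts a known one-sided shift into an estimate of a difference and can be changed cheaply.

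**What to change.** In the first trimming criterion, limit explantation before Month 9 to explantation due to AE or LCE, using the discontinuation reason the protocol already requires on the eCRF (4.7.2, 4.7.3). Then:

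- State explicitly how an explantation for a device problem without an AE is classified. Protocol Table 6 provides for explanting a damaged Implant even where no AE occurred, so the case will need a rule.
- Treat PDS patients explanted for other reasons like the matching ITV exit, with BCVA after explant censored as in the first MMRM analysis. Those with no usable Month 9 or Month 10 value are removed as missing at random.
- Report the current all-explantation rule alongside.
- Because unmasked interim efficacy analyses have already taken place (SAP 4.8), record the change as post-interim and present both versions.

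The cost is a few sentences in the SAP and one more analysis run. The revised rule relies on the recorded reason for discontinuation. Some asymmetry remains: an ITV patient who stops treatment but keeps attending can be a completer, while an explanted PDS patient's later values are censored. LCE is also defined through Implant refills, so in ITV only the AE route can operate. Both should be stated when the result is reported.
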